In the usual care group, the proportion of patients who underwent IAC is a measure of adherence. In the experimental group, the proportion of patients who underwent IAC is of relevance as it reflects the limits of the non-invasive approach.

- The effect of intervention on changes over time of the SOFA score, the blood haemoglobin level, haematocrit, mean daily blood volume drawn for lab testing, mean daily amount of intravenous fluids given for rapid vascular volume expansion, mean daily fluid balance, daily maximum pain and associated 95%CI will be estimated using mixed linear models, after data transformation if necessary.
- Duration of mechanical ventilation will be analysed using a competing risk approach, with death as competing risk.
- The effect of intervention on proportion of patients treated by renal-replacement therapy or by vasopressor, proportions of patients with arterial and central venous catheter-related infections or bloodstream infections and associated 95%CI will be estimated using the competing risk approach, with death as competing risk.
- The effect of intervention on number of blood cultures performed, number of attempts at arterial puncture, number of red blood cell packs transfused, number of arterial and central venous catheter insertion and associated 95%CI will be estimated using negative binomial models with duration of ICU stays as offset variable.
- Two-sided 95% CIs of median differences of free-days (Ventilator-free days, renal replacement therapy-free days, vasopressor therapy-free days) will be estimated.
- Duration of ICU and hospital stay: 2-sided 95% CIs of median differences will be estimated.

- The effect of intervention on ICU and hospital mortality and 95% CI will be estimated using competing-risk model with ICU and hospital discharge alive as competing events with death during the stay.

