The primary analysis of the primary outcome will be the determination of the between-group difference (noninvasive group minus invasive group) in rates of day-28 mortality, estimated with a binomial generalized estimating equation (GEE) model with identity link adjusted on the stratification variables and on the center effect (Pedroza 10.1186/s12874-016-0217-0). A switch from noninferiority to superiority is *a priori* planned if the hypothesis of noninferiority with a noninferiority margin of 5 percentage points is verified. These hypotheses will be assessed using the stratified Farrington-Manning test for differences in proportions.

Secondary outcomes analysis

Statistical analyses for secondary outcomes will not be adjusted for multiplicity; therefore, secondary-outcome findings should be interpreted as exploratory.

- Day-90 mortality will be analyzed with the same model as the primary outcome .
- Cumulative incidence of death from randomization through Day 90 will be analyzed with a Cox model.
- ICU mortality and hospital mortality will be analyzed in a competing risks framework. A hazard ratio will be computed from the whole groups using a Fine and Gray regression model. ICU discharge or hospital discharge will be considered as competing events.

The following outcomes will be described with median and quartiles and compared between groups using median differences:

- Duration of ICU stay from randomization to discharge.
- Duration of hospital stay from randomization to discharge.
- Duration of mechanical ventilation from randomization and Day 28.
- Ventilator-free days from randomization to Day 28.
- Renal replacement therapy-free days from randomization to Day 28.
- Vasopressor therapy-free days from randomization to Day 28.

For each outcome, 95% confidence intervals of the median difference will be computed using unstratified bootstrapping (10,000 samples with replacement). Vasopressor therapy-free days, renal replacement therapy-free days and duration of mechanical ventilation do not account for the competing risk of death.

The following outcomes will be represented with boxplots at each day:

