- Evolution of daily SOFA score during the first seven days after randomization. This outcome will be analyzed with a linear mixed model with time (considered as a quantitative variable) and the intervention group as fixed effects, an interaction term between group and time, and a random effect on the patient. The regression terms will be estimated with their 95% confidence intervals, with the noninvasive group as the reference. The same model will also be analyzed with time considered as a qualitative variable in the aim to describe the mean difference between groups at each time, using contrasts.
- Mean daily blood volume drawn for laboratory testing during ICU stay.
- Evolution of blood hemoglobin level from randomization to Day 28.
- Evolution of hematocrit from randomization to Day 28.
- Daily amount of intravenous fluid given for rapid vascular volume expansion during the first seven days after randomization.
- Daily fluid balance during the first seven days after randomization.

The following outcomes will be analyzed with a difference of proportions:

- Proportion of patients treated by renal-replacement therapy between randomization and Day 28.
- Proportion of patients treated by vasopressor between randomization and Day 28.

The time free of arterial catheter insertion, from randomization through Day 90 will be graphically represented with cumulative incidence curves.

The following outcomes will be analyzed with the use of a quasi-Poisson regression model and expressed as rate ratios, with the duration of stay in the ICU as the offset:

- Number of arterial and central venous catheter insertion during ICU stay from randomization to Day 28.
- Number of blood cultures performed during ICU stay from randomization to Day 28.
- Number of blood draws from the venous catheter during ICU stay from randomization to Day 28.
- Number of attempts at arterial puncture during ICU stay from randomization to Day 28.
- Number of red blood cell packs transfused during ICU stay from randomization to Day 28.
- Numbers of arterial and central venous catheter-related bloodstream infections during ICU stay from randomization to Day 28.

Safety outcomes and analyses

- The number of adverse events of special interest will be described in each group and compared using a chi-squared test.

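### The SAP specifies a model only for SOFA among six daily outcomes; blood volume drawn, haemoglobin, haematocrit, volume-expansion fluid and fluid balance have no between-group estimate, and the change is not recorded

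*SAP*

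**What the plan says.** Protocol 6.2, under the analysis of secondary clinical outcomes, names SOFA, haemoglobin, haematocrit, daily blood volume drawn, volume-expansion fluid, fluid balance and daily maximum pain. It says that the intervention effect on their course over time, with 95% intervals, "will be estimated using mixed linear models, after data transformation if necessary".

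The SAP, under Secondary outcomes analysis, opens a list with "The following outcomes will be represented with boxplots at each day". The first entry is daily SOFA, which carries its own specification: "This outcome will be analyzed with a linear mixed model", with group, time, their interaction, a patient random effect, 95% intervals and contrasts at each time. The other five entries stop at the name of the outcome. The one for blood volume, for example, reads only "Mean daily blood volume drawn for laboratory testing during ICU stay". Those for haemoglobin, haematocrit and volume-expansion fluid are equally bare, and the last entry is just "Daily fluid balance during the first seven days after randomization", again without any method attached.

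The SAP closes with a summary of changes from the initial protocol. It covers the primary analysis, the pain outcome, the handling of competing risks, an added safety analysis, outcomes that cannot be analysed and a removed sensitivity analysis. None of the five outcomes above appears in it.

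**The concern.** A boxplot per day displays a distribution. It does not define a between-group effect or state its uncertainty.

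Less blood drawn is the first benefit that the protocol expects from the noninvasive strategy (synopsis, Expected results; section 5). Sampling that leads to anaemia is part of the rationale (section 1.2), and blood loss is one of the two harms that section 6.1 uses to justify assuming lower mortality in the experimental arm. Protocol 2.2 names fluid balance in secondary objective 1 and the course of haemoglobin in secondary objective 2. On these questions a reader of the results would be left to judge side-by-side plots by eye. Those plots would also show a changing set of patients, because daily follow-up ends at ICU discharge or Day 28 and some patients die before then.

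The lack of a record matters separately. The SAP was amended after blind review and says that some choices were made during the data analysis. A reader cannot tell whether the five models were dropped, when, or why.

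**Working it through.** **Step 1: the six outcomes side by side**

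| Outcome | Protocol 6.2 | SAP | In the SAP's summary of changes? |
|---|---|---|---|
| SOFA | Mixed model, 95% CI | Boxplots and mixed model, 95% CI | Not needed |
| Blood volume drawn | Mixed model, 95% CI | Boxplots | No |
| Haemoglobin | Mixed model, 95% CI | Boxplots | No |
| Haematocrit | Mixed model, 95% CI | Boxplots | No |
| Volume-expansion fluid | Mixed model, 95% CI | Boxplots | No |
| Fluid balance | Mixed model, 95% CI | Boxplots | No |

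Pain is a useful comparison. It stands in the same protocol sentence, and its change of analysis is disclosed, explained and timed in the SAP.

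**Step 2: does another part of the SAP fill the gap?**

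- The SAP's general rule of a two-sided 95% interval for every estimate does not help, because no estimate is defined for these five.
- The model sentence for SOFA is in the singular and sits inside the SOFA entry, so it does not reach the other entries.
- Other SAP lists do name an estimator: median differences, differences of proportions and rate ratios.
- The SAP's list of outcomes that cannot be analysed covers local and catheter-related infections, all bloodstream infections and peripheral venous punctures. None of the five is there, so data quality is not the stated reason.

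**Step 3: is the trial too small for these estimates to be useful?**

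The plan's own sample size comes first. Inputs from Protocol 6.1 are mortality of 22.5% against 25%, a margin of 5 points and 80% power. Protocol 6.2 uses a two-sided 95% interval, hence one-sided 2.5%. Allocation is 1:1 (section 4). The distance to the margin is 0.05 + 0.025 = 0.075.

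n per arm = (1.960 + 0.842)² × (0.225 × 0.775 + 0.25 × 0.75) / 0.075² = 7.849 × 0.361875 / 0.005625 ≈ 505, so 1010 in total. This reproduces the protocol.

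The documents give no SD for the five outcomes, so precision is shown in SD units. Assumptions: a single-day comparison of means, equal arms, normal approximation, and n patients per arm still observed that day.

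Half-width of the 95% CI = 1.96 × √(2/n); difference detectable with 80% power = (1.960 + 0.842) × √(2/n).

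| n per arm observed | Half-width (SD) | Detectable difference (SD) |
|---|---|---|
| 505 (all) | 0.123 | 0.176 |
| 378 (about 75%) | 0.143 | 0.204 |
| 252 (about 50%) | 0.175 | 0.250 |

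The first row is a best case. Protocol 4.6 collects haemoglobin only where a value is available, and follow-up shrinks with death and discharge. Even at half the sample, the estimates would be informative.

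**The case against.** The strongest reply is that the SAP's heading governs display and does not exclude analysis. SOFA sits under the same heading and is modelled as well. The SAP never expressly withdraws the protocol's mixed models, and it amends an earlier published plan that is not among these documents. The models may simply have been left unspecified. This stands in part: the documents show an unreconciled difference, not a proven removal. A reader might infer that the five estimates were dropped deliberately after the data were seen; nothing in the documents supports that. But the SAP is the operative analysis document, it specifies SOFA fully, and it undertakes to list changes from the initial protocol. Silence is therefore not enough.

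Other objections also stand:

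- Volume-expansion fluid and fluid balance are not among the stated expected benefits. Only haemoglobin and fluid balance, of the five, are named in the secondary objectives.
- Related outcomes keep rate ratios in the SAP: red-cell packs, venous-catheter blood draws, arterial puncture attempts, blood cultures and catheter-related bloodstream infections. A reader might infer that the secondary objectives cannot be answered at all. That goes too far, since they have many components; the gap concerns the haemoglobin and fluid-balance components, plus blood volume as an expected benefit.
- Haemoglobin and haematocrit overlap heavily, so five missing estimates are not five independent losses.
- A mixed model uses the same patients as the boxplots and does not remove truncation by death or discharge. Protocol 3.1 discourages routine sampling, so haemoglobin measurement may also be clinically driven.

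**Conclusion.** The point holds as a conflict between protocol and SAP. Five outcomes with a planned effect estimate and interval have neither in the SAP, without record or reason. It matters most for blood volume drawn, then for haemoglobin and fluid balance; it is minor for haematocrit, given its overlap with haemoglobin.

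The reading of the text needs no assumption. The precision figures (half-widths of about 0.12 to 0.17 SD) rest on the assumptions in the working and serve only to show that sample size is not the explanation. They cannot be turned into clinical units without an SD that the documents do not give.

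The point should be corrected but does not threaten the trial. The SAP declares secondary findings exploratory and unadjusted for multiplicity, and neither the non-inferiority conclusion nor the superiority step depends on these outcomes.

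**What to change.** - Extend the SAP's SOFA specification to the five outcomes: group, time, group-by-time interaction, patient random effect, and contrasts with 95% intervals. Keep the boxplots as display. Nothing beyond that model is needed to honour the protocol.
- Transform where needed, as Protocol 6.2 already allows. Do not use a log or square root for fluid balance, which can be negative. A plain log also fails on days with zero volume-expansion fluid.
- State that the estimates describe patients still alive and in ICU with a measurement on the day concerned.
- If any of the five is still not to be modelled, list it in the summary of changes with the reason and the time of the decision. If the SOFA model was always meant to cover the whole list, one sentence saying so settles the matter.

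The cost is a short SAP edit and reuse of existing model code on data that the protocol already collects. The downside is some extra exploratory analysis, read with the truncation caveat.

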4.1. Randomisation

Randomisation will be electronically centralised via a dedicated website.

Randomisation will be stratified on centres, invasive mechanical ventilation (yes or no) and vasopressor dosage, namely < or \geq 0.18 μ g/kg/mn of continuous iv norepinephrine (ie. 0.36 μ g/kg/mn of continuous iv norepinephrine tartrate) or of epinephrine or of the sum of both medications dosages at time of enrolment.

The statistician in charge of the project will determine permutation blocks, the size of which will not be known by the investigators.

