4.5. Study outline

4.6. Schedules of procedures for each enrolled patient

	Inclusion	Short-term follow up until D28 or discharge from ICU (whichever comes first)			Long-term follow up
Study Day 1 starts once patient is randomized		D1, D2, D3	D4, D5, D6, D7	D8 to D28	D90
Inclusion/exclusion criteria	X				
Informed consent	X				
Randomisation	X				
Delayed pursuit consent if applicable		X	X	X	X
Clinical assessment (heart rate, blood pressure, SpO ₂ , pain assessed during transcutaneous vascular puncture ^{a,e} , fluid balance ^b)		X	X	X	
Catheter evaluation (IAC insertion, IAC removal, catheter-related infection)		X	X	X	
Laboratory sampling status (blood volume draw, number of attempts at arterial puncture)		X	X	X	
Therapeutic assessment (number of packs of red blood cells transfused)		X	X	X	
Supportive therapy assessment (respiratory status, ventilator settings ^c , renal replacement therapy ^c , vasopressor support ^b)					
Census evaluation (survival status, in ICU, in Hospital)		X	X	X	X
Specific laboratory testing for the study (SOFA)		X	X		
Blood haemoglobin ^d		X	X	X	
Number of arterial and venous punctures for lab tests, arterial catheter insertion and set up of monitor, blood drawings from arterial catheter or other vascular line, through ICU stay ^e		X	X	X	
Microcosting of staff time and equipment used for arterial and venous punctures for lab tests, arterial catheter insertion and set up of monitor, blood drawings from arterial catheter or other vascular line, through ICU stay ^e		X			
Adverse events/Serious adverse events ^f		X	X	X	X
Query on the French National Hospital Discharge Database (at the end of the study)		X	X	X	

^a: assess by visual or numeric scale for patients able to communicate and by Behavioural Pain Scale(66) otherwise

^b: fluid balance will be assessed only from D1 to D7

^c: if applicable

^d: if available

^e: on a 10% random sample of study population

^f: Collection and reporting of adverse events will begin once the informed consent is signed

Patients' follow-up:

Patients will be examined for signs of shock and organ failures throughout their ICU stay, as done in routine practice.

Their deceased/alive status will be recorded at ICU discharge, hospital discharge, by day 28 and by day 90

Lost-to-follow-up

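### The SOFA mixed model omits the stratification variables, so its group term and daily contrasts have wider intervals than they need

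*SAP*

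**What the plan says.** The SAP's section on secondary outcomes lists "Evolution of daily SOFA score during the first seven days after randomization" and specifies two linear mixed models. The first has fixed effects "with time (considered as a quantitative variable) and the intervention group as fixed effects", then "an interaction term between group and time, and a random effect on the patient". The second treats time as categories "in the aim to describe the mean difference between groups at each time, using contrasts". The regression terms are to be reported with 95% confidence intervals. No starting score, stratification factor or centre appears in either version.

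Protocol 6.2 states the target as "The effect of intervention on changes over time of the SOFA score" and names no covariate for it.

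Protocol 4.1 says "Randomisation will be stratified on centres, invasive mechanical ventilation (yes or no) and vasopressor dosage". The SAP adjusts the primary mortality analysis for the stratification variables and the centre effect, uses the same model for day-90 mortality, and cites methodological recommendations for doing so in its summary of changes. It gives no reason for leaving these variables out of the SOFA model.

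In the schedule of Protocol 4.6, the row "Specific laboratory testing for the study (SOFA" is marked for D1–D3 and D4–D7, with no mark readable under Inclusion. The same table states "Study Day 1 starts once patient is randomized". The SAP says that secondary findings are exploratory and not adjusted for multiplicity.

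**The concern.** Ventilation status and vasopressor dose bear directly on the respiratory and cardiovascular parts of SOFA, so they should predict the score. When randomisation is stratified on prognostic variables and the model ignores them, the model-based standard error still counts variation that the design has already removed from the between-arm comparison. The estimates stay valid, but the intervals around them tend to be too wide.

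The affected quantities are ones the SAP will report: the group term (with an interaction in the model, the between-arm difference at time zero) and the difference at each day. What is at stake is precision on a secondary organ-failure outcome, and consistency with the SAP's own treatment of mortality.

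**Working it through.** **Inputs.** From the documents: 1010 patients, 1:1 allocation, seven daily scores, a random patient effect. Assumed, because the documents give neither: SOFA SD of 3–4 points and a constant correlation ρ between any two scores of one patient. Also assumed: the share R² of SOFA variance explained by the strata. Steps 2–5 assume complete data.

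**1. The plan's own figure.** Protocol 6.1 assumes mortality of 22.5% and 25%, a margin of 5 points and 80% power. With one-sided 2.5%, n per arm = (1.960 + 0.842)² × (0.225×0.775 + 0.25×0.75) / (0.05 + 0.025)² = 7.85 × 0.3619 / 0.005625 ≈ 505, so 1010 in total. The stated size reproduces. It concerns mortality and does not depend on the SOFA model; it supplies the 505 per arm used below. There is no stated SOFA figure to reproduce.

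**2. Day contrast.** In SD units, SE = √(2/505) = 0.0629 unadjusted and √(2(1 − R²)/505) adjusted. The reduction is 1 − √(1 − R²).

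| R² | adjusted SE | reduction | 95% half-width, SD 3 to 4 |
|---|---|---|---|
| 0 | 0.0629 | – | 0.37 to 0.49 points |
| 0.10 | 0.0597 | 5% | 0.35 to 0.47 points |
| 0.30 | 0.0527 | 16% | 0.31 to 0.41 points |

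If the strata correlate only 0.2–0.3 with SOFA (R² of 0.04–0.09), the reduction is 2–5%.

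**3. Direction of the error.** If the strata are close to balanced, the true sampling variance of the unadjusted contrast is already near the adjusted one, while the model reports the larger figure. The reported interval is then too wide by 1/√(1 − R²) − 1, which is 5% at R² = 0.10 and 20% at R² = 0.30. The effective multipliers are 1.96/√0.9 = 2.07 and 1.96/√0.7 = 2.34, so a nominal 95% interval covers about 96% to 98%.

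**4. Group term.** With seven equally spaced days, Var = (2/505) × [B + (1 − ρ)(1/7 + t̄²/28)], where B is the between-patient variance (ρ unadjusted, ρ − R² adjusted) and t̄ is the mean day. Take ρ = 0.5.
- Days coded 0–6 (t̄ = 3): the bracket is 0.732 unadjusted, 0.632 at R² = 0.10 and 0.432 at R² = 0.30. The SE falls by 7% and 23%.
- Days coded 1–7 (t̄ = 4): the bracket is 0.857, 0.757 and 0.557. The SE falls by 6% and 19%.

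**5. Group-by-time term.** Var = 2(1 − ρ)/(505 × 28). B does not enter, so a patient-level covariate changes nothing: at ρ = 0.5 the SE is 0.0084 SD per day either way. In simulation this term was uncorrelated with the chance difference in starting score (about −0.02). With random slopes, or a correlation that changes over time, this would be approximate.

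**6. A true baseline SOFA, if one exists.** The reduction for a day contrast is 1 − √(1 − ρ²): 13% at ρ = 0.5 and 29% at ρ = 0.7. These are upper values. If observation falls linearly to 50% by Day 7 through death or ICU discharge (assumed), the Day 7 reduction drops to 9% and 21%, because the mixed model already borrows from each patient's earlier scores. The gain from the strata erodes on later days for the same reason.

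**The case against.** The strongest reply is that the term closest to the protocol's target, change over time, is the group-by-time interaction, and that it loses nothing under the specified model. That is correct and limits the point to the group term and the day contrasts. Both are still reported with intervals or contrasts, so the point does not vanish.

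A second reply is that stratified randomisation already protects against imbalance on ventilation and vasopressor dose. That also stands, and it is why the consequence is conservative intervals and not misleading estimates.

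A reader might infer something stronger: that omitting a starting SOFA biases the comparison, or lets chance imbalance pass for a treatment effect. The documents do not support this. Imbalance after randomisation is random, and the unadjusted interval allows for it. A reader might also take the 13–29% gain as available. It requires a SOFA score taken before randomisation, and the readable schedule shows none. Day 1 begins at randomisation, so a Day 1 score may be one of the outcomes, and adjusting for it could remove part of an early effect.

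The size is uncertain too: two binary strata may explain little, and the only centre figure given, an intra-class correlation of 0.02, is for day-28 mortality and not SOFA. Extending the point to haemoglobin and haematocrit would be conditional, since the SAP lists those only under boxplots.

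**Conclusion.** The point holds as a modest efficiency and consistency matter. The SOFA model ignores variables that structured the randomisation and that the same SAP uses for mortality. If the strata explain 10–30% of SOFA variance, the standard error of a day contrast falls by about 5–16% with complete data; weaker strata give less, and so do later days. The group-by-time term is essentially unaffected under the specified random-intercept model. The estimates are not biased. SOFA is an exploratory secondary outcome, so neither the primary conclusion nor any trial decision changes.

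**What to change.** Add invasive ventilation, vasopressor-dose stratum and centre to both versions of the SOFA model, in line with the mortality analyses. Because the SAP was amended after the blind review in December 2024, label the adjusted model as added after that review and report the specified model beside it.

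State whether a SOFA score measured before randomisation was recorded. If it was, add it as a covariate as well. If the first score is a Day 1 value that may be post-randomisation, do not use it as a covariate. Say in the report that the group term is the difference at time zero and give the day coding.

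The cost is a few lines of code. The strata were needed to randomise each patient, so no new data are required and the primary analysis is untouched.

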Deferring arterial catheterization in critically ill patients with shock – EVERDAC trial

STATISTICAL ANALYSIS PLAN — December 2024

The initial Statistical Analysis Plan established before launching the study and published in BMJ Open in 2021 ([name] et al. BMJ Open 2021;11:e044719. doi:10.1136/bmjopen-2020-044719) was amended after the blind review of the data in December 2024.

Level of statistical significance

Statistical significance threshold will be set at 5%, and 95% two-sided confidence intervals (95%CI) will be calculated for all estimates.

Analyzed population

All randomized patients, except for patients who secondarily object to the use of their data or protected under guardianship, will be included in the analysis. No interim analysis will be performed.

Two per-protocol populations were defined during the blind review:

- In the first per-protocol population, we will exclude patients wrongly included, and patients from the noninvasive group in whom the arterial catheter previously inserted was not removed after the randomization. In the invasive group, we will exclude the patients who either did not undergo an attempt at arterial catheter insertion or had the arterial catheter insertion more than 24h after randomization.
- In the second per-protocol population, we will exclude patients from the invasive group who did not receive an arterial catheter within 24h after randomization, regardless of the reason (unsuccessful arterial catheter insertion, no attempt of arterial catheter insertion or insertion occurring more than 24h after randomization). The per-protocol population in the noninvasive group will remain unchanged for the second per-protocol analysis.

Description of baseline characteristics

All data recorded at baseline will be summarized by treatment group using means and standard deviation for normally distributed quantitative variables, median and interquartile range for other quantitative variables, and counts and percentages for qualitative variables. No statistical test will be used.

Primary outcome

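### Read as a random patient intercept, the linear-time SOFA model gives too narrow a confidence interval for group-by-time if patients' slopes differ or their daily residuals are correlated

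*SAP*

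**What the plan says.** The SAP, under Secondary outcomes analysis, takes the "Evolution of daily SOFA score during the first seven days after randomization" and fits a "linear mixed model with time (considered as a quantitative variable) and the intervention group as fixed effects", with "an interaction term between group and time, and a random effect on the patient". On inference it says that "The regression terms will be estimated with their 95% confidence intervals". It then adds a second version: "The same model will also be analyzed with time considered as a qualitative variable", used for group contrasts on each day. It names no random slope, no residual correlation structure and no robust variance.

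Protocol section 6.2 does not fill the gap. It says only that the effect on SOFA and several other repeated measures "will be estimated using mixed linear models, after data transformation if necessary". The SAP's section on the level of significance applies to this model as to the others: "Statistical significance threshold will be set at 5%, and 95% two-sided confidence intervals (95%CI) will be calculated for all estimates".

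**The concern.** The quantity of interest is the difference between arms in SOFA slope. If the only random term is one intercept per patient, the model assumes that all patients in an arm share one slope and that, given the intercept, daily residuals are independent. When patients recover or deteriorate at different rates, the slope variance goes into the residual. The model then treats it as day-level noise instead of variation between patients, and the standard error of group-by-time comes out too small. Serial correlation between neighbouring days acts in the same direction.

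Organ failure progression is part of the first secondary objective (Protocol section 2.2). An interval that is too narrow can mislead in two ways: it can suggest a difference in trajectory that is not there, or it can overstate how precisely a difference near zero has been shown.

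**Working it through.** **Inputs from the documents.** Seven daily scores; linear time, group, group-by-time and a patient effect; two-sided 5% level (SAP). 1010 patients allocated 1:1 (Protocol sections 6.1 and 4). The documents give no SD, slope variance, day-to-day correlation or power for SOFA, so there is no SOFA figure to reproduce. The sample size does reproduce: (1.96 + 0.8416)² × (0.225 × 0.775 + 0.25 × 0.75) / 0.075² = 504.9, so 505 per arm and 1010 in total. It is used here only as the simulated trial size.

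**Assumed.** Residual SD s = 1.5 points (range 1.0 to 2.0); SD t of patient slopes from 0 to 0.7 points per day.

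**Formula.** Centred days −3 to 3 have sum of squares 28. With complete data:
- true variance of one patient's fitted slope: t² + s²/28
- residual variance under the intercept-only model: s² + 28t²/6 = s² + 4.667t²
- variance of the slope that this model reports: t²/6 + s²/28
- ratio of true to reported variance: (s² + 28t²)/(s² + 4.667t²)

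The ratio exceeds 1 for any t above 0 and does not contain the number of patients. Example, t = 0.3: (2.25 + 2.52)/(2.25 + 0.42) = 1.787. The standard error is too small by √1.787 = 1.34, and P(|Z| > 1.96/1.34) is 14.3%.

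| Slope SD (s = 1.5) | SE too small by | True rejection rate | Simulated, complete data | Simulated, 10% daily exit |
|---|---|---|---|---|
| 0 | 1.00 | 5.0% | 5.5% | 4.9% |
| 0.1 | 1.05 | 6.2% | 5.3% | not run |
| 0.2 | 1.18 | 9.6% | 9.1% | 9.9% |
| 0.3 | 1.34 | 14.3% | 15.0% | 13.4% |
| 0.5 | 1.65 | 23.4% | 25.8% | 24.7% |
| 0.7 | 1.88 | 29.6% | not run | not run |

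Simulations used 1010 patients, no group effect and 1500 runs per setting; exit was unrelated to SOFA. For slope SD 0.1 to 0.7, the formula gives 7.6% to 35.4% at s = 1.0 and 5.7% to 24.3% at s = 2.0. The ceiling is a variance ratio of 6, which means 42%. The rate stays at or below 6% if t/s is under about 0.06 (0.09 points per day at s = 1.5), and it passes 10% at about 0.14 (0.21 points per day).

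**Serial correlation without slope variation.** The ratio is (c′Rc/28)/(1 − r̄), where c holds the centred days, R is the AR(1) correlation matrix and r̄ is the mean correlation between different days. At ρ = 0.5: (43.22/28)/(1 − 0.239) = 2.03, SE factor 1.42, rejection 16.9%. At ρ = 0.3, 0.7 and 0.8 the rate is 11.3%, 22.8% and 25.7%.

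**Categorical time, single-day contrasts.** With complete data, the intercept-only standard error uses the total variance averaged over the seven days. Assume intercept SD 3 on day 1 and no intercept-slope correlation. At t = 0.3 the total variance is 9 + 2.25 = 11.25 on day 1, 11.25 + 0.09 × 36 = 14.49 on day 7, and 11.25 + 0.09 × 13 = 12.42 on average. The ratios 0.906 and 1.167 give 3.9% and 7.0%. At t = 0.5 the ratios are 11.25/14.50 and 20.25/14.50, giving 2.6% and 9.7%. Averages over days are 5.0% and 5.1%. With an intercept-slope correlation of −0.3 at t = 0.3, the range is only 4.6% to 5.5%.

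**Categorical time, change between days.** For day 7 minus day 1 the ratio is (36t² + 2s²)/[2(s² + 4.667t²)], which is 7.74/5.34 at t = 0.3 and 13.5/6.83 at t = 0.5. Rejection is about 10% and 16%.

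**After the fix.** With complete data, the random-slope test equals a t-test on patient slopes: 4.9% to 5.5% for slope SDs 0.1 to 0.5, and 5.1% under AR(1) with ρ = 0.7 (4000 runs each). The intercept model with patient-clustered standard errors gives 4.2% to 6.1% in all 13 simulated settings, including those with exit. The random-slope model under exit was checked less thoroughly: 4.5% and 3.5% in 200 runs each at slope SD 0.3 and 0.5, and 1 rejection in 84 further runs at 0.3. None of these shows inflation.

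**The case against.** - **The random structure is inferred.** The SAP writes neither intercept nor only, so a reader might conclude too firmly that a random slope has been ruled out. This stands as a limit on the claim. One unqualified patient effect is still most naturally an intercept, and if something else is meant the SAP needs to say so.
- **The size is assumed.** A reader might infer that false positives are in fact well above 5%. The documents cannot support that, because they give no SOFA variance components and the low end of the range is 5.0%. What supports the direction is the population. Entry covers hypotension alone as well as vasopressor use up to the exclusion limit (Protocol section 4.3), and assumed day-28 mortality is 22.5% to 25% (section 6.1). One common slope per arm is therefore unlikely.
- **The categorical version.** A reader might infer that it has the same defect. For the daily contrasts that the SAP plans, it does not: slope variance is not divided down, and unequal correlation between days does no harm if the total variance is equal on all days. Only contrasts of change between days inherit the problem, and the SAP does not announce any. The daily contrasts and boxplots also mean that readers do not depend on the slope term alone.
- **Low stakes.** The SAP plans intervals and no explicit SOFA test, and says that "secondary-outcome findings should be interpreted as exploratory". That limits the consequence. But the label answers multiplicity; it does not make a nominal 95% interval cover 95%.

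**Conclusion.** The point holds conditionally. If the patient effect is an intercept and standard errors are model-based, the group-by-time interval is too narrow whenever slopes vary or residuals are serially correlated, and recruiting more patients does not change this. At an assumed residual SD of 1.5, coverage falls from 95% with no slope variation to about 86% at slope SD 0.3 and 77% at 0.5 (100% minus 14.3% and 23.4%). Inflation is the likely direction; its size is not known from the documents. Single-day contrasts from the categorical version are miscalibrated by a few percentage points and average near 5%.

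The consequence is confined to one exploratory secondary outcome. The day-28 mortality analysis is untouched. All figures assume that patients leave observation for reasons unrelated to SOFA. The SAP states no handling of death or discharge in this model, and that is a separate issue.

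**What to change.** State the random structure explicitly. In the quantitative-time model, either add a random slope for time, correlated with the intercept, or keep the intercept and report patient-clustered robust standard errors. In the categorical-time model, use an unstructured within-patient covariance, or at least one that lets the variance differ by day.

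The cost is one model term or one variance option in the SAP and code. The group-by-time interval widens by roughly the factor by which its standard error was understated: nothing if slopes do not vary and residuals are independent, and 1.05 to 1.88 over the assumed slope SDs of 0.1 to 0.7. If the random-slope model does not converge, the clustered standard errors are the ready alternative. The change does not deal with death or discharge related to SOFA.
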